## Hypothesis of the Clinical Investigation

1. VRelax will reduce acute stress: the PRE-VAS score will be higher than the POST-VAS score.
2. VR relaxation will have a greater relaxing effect than standard relaxation: VAS scores and biomarkers will reflect a stronger relaxation effect.
3. VRelax will also reduce chronic stress through a cumulative effect, meaning the post-intervention PSS score will be lower than the pre-intervention PSS score.
4. There will be a difference in the acute effect over time; in other words, as the number of sessions increases, habituation or boredom may occur for both standard and VR relaxation. This will be measured by a decreasing difference between pre- and post-VAS scores per individual over time.

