## **7. Objective of the Clinical Investigation**

### **7.1 Primary Objectives**

The main objective is to examine the relaxing effect of VRelax. We aim to measure the magnitude and duration of the effect and assess the difference compared to standard relaxation exercises. What is the immediate effect, and what is the long-term impact? Is there any habituation? Which physiological parameters are most influenced?

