## **13. Methodology**

### **13.1 Study-Specific Procedures**

The study consists of two blocks of 10 sessions: one block with VR and one without. Each participant thus serves as their own control.

The control sessions take place in the VR room, seated, with a total duration of 30 minutes (including 20 minutes of relaxation of their choice, e.g., reading, listening to music, watching a short film, body scan, etc.). The selected relaxation method is recorded for each session.

The VR sessions also take place in the VR room, seated, with a duration of 30 minutes (including 20 minutes of VRRelax with one or more 360° videos of the participant's choice). Guided meditation sessions are excluded, as they require the eyes to be closed. The selected videos are recorded per session.

Before and after each session, stress is assessed using VAS scores for stress/tension and happiness. At the beginning and end of each 10-session block, general stress levels are measured using the Perceived Stress Scale (PSS). After the final session of each block, a structured qualitative interview is conducted regarding the user experience. All groups receive the same pre- and post-intervention assessments.

During each relaxation session, physiological parameters are also measured using the Embrace Plus device ([www.Empatica.com](http://www.Empatica.com)), including heart rate, heart rate variability (HRV), respiratory rate, skin conductance, and skin temperature.

---

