## Study Analysis

### 16.1 Sample Size Calculation

The primary endpoint selected was a change in the VAS score for relaxation, where an average improvement of 0.5 out of 10 is considered clinically relevant.

The standard deviations used (0.83 for standard relaxation and 0.74 for VRelax) were estimated based on the results of a comparable study in an outpatient setting, as described in the article by Veling et al. (2021).

The chosen statistical power was 80%, and the type I error rate (alpha) was set at 0.05.

Calculations were performed using the software program **GPower**.

To determine the required sample size using the VAS relaxation score as the primary outcome measure:

- With an expected dropout rate of 30%, the final **sample size = 54**.

---

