**1 - (VAS score before / VAS score after)**

Descriptive statistics (mean, standard deviation, minimum, and maximum) will be computed for demographic, clinical, and outcome variables.

VAS scores for relaxation and happiness, as well as physiological parameters (heart rate, HRV, skin conductance, respiration), will be compared using **paired t-tests** between pre- and post-session time points.

Perceived Stress Scale (PSS) scores will also be compared between pre- and post-therapy blocks (each block consisting of 10 sessions) using a paired t-test.

To estimate the difference in effect between the VR treatment and standard relaxation, a **mixed model multilevel regression analysis** will be used. The model will include:

- Time (before vs after)
- Treatment (VR vs standard)
- Group (1 vs 2)
- Interaction term: Time × Treatment  
(with random intercept for “participant”)

The **interaction between time and treatment** is the primary parameter of interest.

Finally, **carry-over effects** will be examined by comparing VAS scores and physiological parameters between session 1, session 5, and session 10 using paired t-tests (S1 vs S5 and S5 vs S10).

---

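### Habituation (hypothesis 4) has no adequate analysis in section 16.2: there is no session term, and the only across-session tests use 3 of the 10 sessions

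*Combined protocol and SAP*

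**What the plan says.** Item 4 under Hypothesis of the Clinical Investigation predicts habituation or boredom, for VR and for standard relaxation, as sessions accumulate: "This will be measured by a decreasing difference between pre- and post-VAS scores per individual over time". Section 7.1 puts the same question among the primary objectives: "Is there any habituation".

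The data for an answer are planned. Section 13.1 states: "The study consists of two blocks of 10 sessions: one block with VR and one without", and "Before and after each session, stress is assessed using VAS scores for stress/tension and happiness". Each participant who completes therefore gives ten pre-post VAS changes per block.

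Section 16.2 lists four kinds of analysis:

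- paired t-tests of pre against post, within session;
- a paired t-test of the PSS before and after a block, which is a different scale;
- a mixed model whose time factor is "Time (before vs after", with treatment, group, time by treatment and a random participant intercept;
- a final step in which "carry-over effects will be examined by comparing VAS scores and physiological parameters"; the sessions and tests chosen for this step are given as "between session 1, session 5, and session 10 using paired t-tests (S1 vs S5 and S5 vs S10".

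Only the last looks across sessions on the VAS. No analysis is named for hypothesis 4, no size or shape of habituation is given, and no rule says how the two tests are to be read together.

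**The concern.** A stated hypothesis and primary-objective question is left either with no test, if the S1/S5/S10 comparisons really are about carry-over, or with a weak one, if they are meant to serve for habituation. Read the second way, they leave out seven of the ten sessions, never compare the first with the last, and do not ask whether VR and standard relaxation fade at different rates. As worded they compare VAS scores, whereas hypothesis 4 concerns the pre-post difference.

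Section 7.2 says the trial is to inform whether investment in VR is justified. Whether the effect lasts over repeated use bears on that decision. Two non-significant half-block tests could be taken as evidence of a stable effect when the design had little chance of showing otherwise.

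**Working it through.** **The plan's own figure.** Section 16.1 gives SDs of 0.83 and 0.74, a difference of 0.5, alpha 0.05, power 80% and 30% dropout, leading to 54. A two-sided paired t-test with zero correlation (not stated in the plan) has SD of the difference √(0.83² + 0.74²) = √1.2365 = 1.112. This needs n = 41, and 41 × 1.3 = 53.3, so 54. The figure is reproduced, but it concerns VR against standard relaxation and says nothing about habituation. With 30% dropout, 54 × 0.7 = 37.8, so about 38 completers.

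**Assumptions for habituation.** n = 38; the SD of a single-session pre-post change is σ = 0.74 (the plan's VRelax figure, assumed to apply per session); common between-session correlation ρ of 0, 0.3 or 0.5; one block; two-sided 0.05. The outcome is the pre-post difference, as hypothesis 4 words it. Total decline D is 0.5 or 0.25 points, linear over sessions 1 to 10. The plan gives no D, shape or ρ.

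**Formulas.** Let s = σ√(1−ρ).

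- Two-session contrast: SD per patient s√2. S1 vs S5 spans 4/9 of D, S5 vs S10 spans 5/9, S1 vs S10 all of it.
- Ten-session slope: D/9 per session. SD per patient s/√82.5, where 82.5 is the sum of squared deviations of 1 to 10 from 5.5.
- Power from the noncentral t with 37 degrees of freedom and noncentrality effect ÷ (SD/√38).

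**Numbers for D = 0.5, ρ = 0.** The contrast standard error is 0.74 × √2 / √38 = 0.170.

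- S1 vs S5: 0.222/0.170 = 1.31, power 25%.
- S5 vs S10: 0.278/0.170 = 1.64, power 36%.
- S1 vs S10: 0.5/0.170 = 2.94, power 82%.
- Slope: 0.0556 ÷ (0.0815/√38) = 0.0556/0.0132 = 4.2, power 98%.

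The either and both figures come from simulation.

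| Power, ρ = 0 / 0.3 / 0.5 | D = 0.50 | D = 0.25 |
|---|---|---|
| S1 vs S5 | 25 / 33 / 44% | 10 / 12 / 15% |
| S5 vs S10 | 36 / 48 / 62% | 13 / 16 / 20% |
| Both significant | 4 / 10 / 20% | under 1% |
| Either significant | 57 / 72 / 86% | 22 / 27 / 34% |
| S1 vs S10 | 82 / 93 / 98% | 30 / 40 / 53% |
| Ten-session slope | 98 / >99 / >99% | 54 / 69 / 83% |

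With no decline, at least one of the two unadjusted tests is significant in about 9% of trials. With SD 0.83, either is 49/62/77% at D = 0.5 and 19/23/29% at D = 0.25.

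**Efficiency.** If all patients share a slope, its variance from S1 and S5 alone is (2/16)/(1/82.5) = 10.3 times that of the ten-session slope, and from S5 and S10 alone (2/25)/(1/82.5) = 6.6 times. These ratios do not depend on σ, n, D or ρ. If slopes vary between patients (ρ = 0, D = 0.5), ten-session power falls to 94% at a slope SD of 0.05 per session and to 73% at 0.10. At 0.10, either planned test gives about 48%, and the variance ratios are 4.7 and 3.2.

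**Other shapes (D = 0.5, σ = 0.74).**

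- Early decline, half-life two sessions: S1 vs S5 63-89%, slope 96% or more.
- Decline only after session 5: S5 vs S10 81-98%, slope 99% or more.
- Whole loss between sessions 1 and 2, ρ = 0: S1 vs S5 keeps the full 0.5 and has 82%. The fitted slope is 0.5 × 4.5/82.5 = 0.0273 per session, noncentrality 0.0273/0.0132 = 2.06, power 52%.

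**The case against.** A reader might infer that the plan would usually miss habituation and report none. The documents do not support that. At a decline of 0.5, at least one planned test is significant in 57-86% of trials with SD 0.74, which is more often than not. Missing it is the usual outcome only under other conditions: a smaller decline such as 0.25, a requirement that both tests be significant, or less favourable variances (SD 0.83 with uncorrelated sessions, or widely varying slopes). The plan fixes none of these.

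Nor are all declines cut in half by the two contrasts. That describes a roughly linear decline; an early or late drop falls mainly within one contrast. The slope is not uniformly better either, since it loses to S1 vs S5 when the whole loss comes straight after session 1.

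The 0.5 used here is not the trial's threshold for habituation. The statement that "an average improvement of 0.5 out of 10 is considered clinically relevant" refers, in section 8.1, to change within a session. And section 16.2 names time by treatment as the parameter of main interest, so the primary endpoint is untouched.

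All of this stands, and it limits what can be claimed about the size of the loss. It does not supply the missing analysis. The carry-over label helps least: if the tests are not for habituation, hypothesis 4 has no test at all.

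**Conclusion.** The point holds in limited form. Section 16.2 assigns no analysis to hypothesis 4. What could stand in for one uses three of ten sessions, omits S1 vs S10, and cannot compare decline between treatments. For a gradual linear decline it is much less powerful than a slope through all ten sessions, and reading either test as sufficient also raises the false-positive rate to about 9%.

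The absence of an assigned analysis rests on the text alone. The power figures rest on assumed values for the size and shape of the decline, the session-level SD and the between-session correlation, and should be read as illustrations. A larger single-session SD would lower all of them. This should be corrected before the data are analysed; it does not threaten the primary comparison.

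**What to change.** In section 16.2, name a test for hypothesis 4. Take the per-session pre-post VAS change from all ten sessions of both blocks and fit a mixed model with session number (1 to 10), treatment, session by treatment, and a random participant slope alongside the existing random intercept. Report the slope under each treatment and their difference, with confidence intervals. A mixed model is preferable to one least-squares slope per patient, because the two agree only with balanced data and 30% dropout is expected.

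Keep S1 vs S5 and add S1 vs S10 as supportive contrasts of the pre-post change, since the linear term is weaker for an abrupt early loss. Plot the ten session means by treatment to check the shape. If the S1/S5/S10 comparisons are also meant to address carry-over, say so separately.

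The cost is a change of wording, a linearity assumption and slightly more analysis work. No new data, visits or participants are needed. Power for the session by treatment term has not been worked out here and should be stated when the term is added.

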## 17. Final Clinical Investigation Report

Within one year after the final completion of the clinical investigation, the sponsor will prepare a comprehensive final report.

In case of early termination, the report will be submitted within 3 months after LPLV (Last Patient Last Visit).

The report will include a critical evaluation of all collected data and will also address any negative findings.

---

## 18. Publication Policy

This study will be registered in a public clinical trial registry prior to the inclusion of the first subject. The study results will also be submitted to this public registry.

## 19. Indemnity insurance

During their participation in the study the patients will be insured as defined by legal requirements. An insurance with no fault responsibility has been foreseen for the Belgian participants by the sponsor in accordance with the Belgian law of 22 december 2020 concerning medical devices.

## 20. Authorization of the clinical investigation

This study must obtain approval from the IEC prior to the start of the study. Any additional requirements imposed by the IEC shall be followed. Substantial protocol amendments will be notified to the IEC during the course of the study according to the requirements and within the timelines as defined by the national law.

## 21. Protocol compliance

Prospective, planned deviations or waivers to the CIP are not allowed. Under emergency circumstances, deviations from the CIP to protect the rights, safety or well-being of human subjects may proceed without prior approval of the sponsor and the IEC. Such deviations shall be documented and reported to the sponsor by email ([[contact]](mailto:[contact]) and [[contact]](mailto:[contact])) and the IEC as soon as possible. Accidental protocol deviations must be adequately documented and reported in the eCRF on the protocol deviation log. In case accidental protocol deviations are considered as critical issues that significantly affect patient safety, data integrity and/or study conduct these should be reported to the sponsor immediately by email ([[contact]](mailto:[contact]) and [[contact]](mailto:[contact])). The sponsor will subsequently communicate and discuss this with the IEC.

The following items will be documented on the protocol deviation log: date of deviation, description of deviation, actions taken and classification of deviation. Deviations will be classified as minor or major. A minor protocol deviation is a deviation that does not affect the safety, rights or well-being of subjects or the quality of their data. A major protocol deviation is a deviation that affects safety, rights or well-being of subjects or quality of their data.

Any deviation that potentially interferes with and/or affects the efficiency and/or quality conduct of the study will be discussed by the monitor with the PI and will be documented on the monitoring report including a proposed plan of action for resolution if applicable.

## 22. Good Clinical Practice (ISO 14155)

This study will be conducted in accordance with the protocol, ISO 14155 which addresses good clinical practices and applicable national and European legislations including but not limited to the General Data Protection Regulation EU2016/679 ("GDPR"), the EU Medical Device Regulation MDR 2017/745, the Belgian royal decree of 18 May 2021 concerning clinical investigations of medical devices and the Belgian law of 22 Dec 2020 concerning medical devices.

ISO 14155 is an international ethical and scientific quality standard for designing, conducting, recording and reporting clinical investigations that involve the participation of human subjects. Compliance with this standard provides public assurance that the rights, safety and well-being of study subjects are protected, consistent with the principles that have their origin in the Declaration of Helsinki, and that the study data are credible.

## 23. Subject information and informed consent

### 23.1. Recruitment and informed consent procedure

Prior to entry in the study, the investigator will explain to potential subjects or their legal representatives the study and the implication of participation. Subjects will be informed that their participation is voluntary and that they may withdraw consent to participate at any time. Participating subjects will be told that their records may be accessed by competent authorities and by authorized persons without violating the confidentiality of the subject, to the extent permitted by the applicable law(s) and/or regulations. By signing the Informed Consent Form (ICF), the subjects or legally acceptable representatives are authorizing such access.

After this explanation and before entry to the study, written, dated and signed informed consent should be obtained from the subject or legally acceptable representative. The ICF should be provided in a

language sufficiently understood by the subject. Subjects must be given the opportunity to ask questions.

The subject or legally acceptable representative will be given sufficient time to read the ICF and to ask additional questions. After this explanation and before entry to the study, consent should be appropriately recorded by means of either the subject's or his/her legal representative's dated signature or the signature of an independent witness who certifies the subject's consent in writing. After having obtained the consent, a copy of the ICF must be given to the subject.

Subjects who are unable to comprehend the information provided can only be enrolled after consent of a legally acceptable representative.

The participant or the participant's legally acceptable representative will be informed in a timely manner if information becomes available that may be relevant to the participant's willingness to continue participation in the study.

### 23.2. Compensation for study participants

Er wordt geen vergoeding gegeven aan de deelnemers. Het voordeel voor de deelnemers is dat zij gratis 20 relaxatiesessies aangeboden krijgen door deel te nemen aan de studie.

## 24. Data Handling

### 24.1. Data collection and processing

Data collection and processing will be done in full compliance with the European Regulation 2016/679 of 27 April 2016 on the protection of natural persons with regard to the processing of personal data and on the free movement of such data (GDPR).

### 24.2. Case Report Form (CRF)

The source documents are to be completed at the time of the subject's visit. The eCRFs are to be completed within reasonable time after the subject's visit. Only the data required by the protocol are captured in the eCRF. For this study both an electronic data capture system (eCRF) and a paper CRF will be used. REDCap is provided and maintained by Vanderbilt University; a license for use was granted to the Health, Innovation and Research Institute (HIRUZ). REDCap is a web-based system.

The study site staff is responsible for data entry in REDCap. For each subject enrolled the eCRF will be signed by the principal investigator or co-investigator. This also applies to those subjects who fail to complete the study. If a subject withdraws from the study, the reason must be noted on the eCRF. CRF entries and corrections will only be performed by study site staff, authorized by the investigator and in accordance with ISO 14155.

The entries will be checked by trained personnel and any errors or inconsistencies will be changed immediately.

The Principal investigator must verify that all data entries in the eCRFs are accurate and correct. If certain information is Not Done, Not Available or Not Applicable, "N.D." or "N.AV." or "N.AP", should be entered in the appropriate space.

**[name]** (affiliated with the Psychiatric Center Sint-Jan Baptist and Ghent University) will conduct the study at Sint-Jan Baptist. All questionnaires and VAS scores will be collected on paper. Measurements obtained via the Embrace Plus device will be stored on a secure server of the manufacturer (Empatica), with access to the raw data restricted to the investigator only.

The data will be entered into **REDCap**, and subsequently also stored on a designated location on the PC Sint-Jan Baptist server, accessible only to the study investigators. Data monitoring and verification will be carried out by the investigator, [name]. **Pseudonymisation codes** will be accessible only to the researchers of the Sint-Jan Baptist Hospital.

#### 24.3. Data directly collected in the CRF (no source available)

The questionnaires will be administered on paper. The physiological data from the Embrace Plus device will be stored in a cloud environment that is accessible only to the investigator, [name].

#### 24.4. Access to source data / documents

The investigator will permit audits, IEC review, and regulatory inspection(s), providing direct access to source data/documents.

#### 24.5. Archiving

The investigator and sponsor specific essential documents will be retained for at least 10 years. At that moment, it will be judged whether it is necessary to retain them for a longer period, according to applicable regulatory or other requirement(s).

### 25. Quality assurance and periodic monitoring

The investigator will maintain adequate and accurate records to enable the conduct of the study to be fully documented and the study data to be subsequently verified. These documents will be classified into two different categories: investigator's file, and subject clinical source documents.

The investigator's file will contain the documents as per EUROPENAN Standard of EN ISO 14155 (incl. GCP) and local regulations.

Data will be evaluated for compliance with the protocol and accuracy in relation to source documents. Following written standard operating procedures, will verify that the clinical investigation is conducted and data are generated, documented and reported in compliance with the protocol, ISO 14155 and the applicable regulatory requirements. The frequency, extent and nature of the monitoring will depend on the risk assessment of the study. The monitor will be working according to SOPs and will provide a monitoring report after each visit for the sponsor and a follow-up letter to the investigator. Depending on the quality of the data, additional monitoring visits will be necessary according to the sponsor's discretion.
